##### 7.1.2 Serious Adverse Event

If the adverse event meets any of the criteria below, it is regarded as a serious adverse event.

- a) Led to a death,
- b) Led to a serious deterioration in health of the subject, that either resulted in
  1. a life-threatening illness or injury, or
  2. a permanent impairment of a body structure or a body function, or
  3. in-patient hospitalization or prolongation of existing hospitalization, or
  4. medical or surgical intervention to prevent life threatening illness or injury or permanent impairment to a body structure or a body function.
  5. chronic disease
- c) Led to fetal distress, fetal death or a congenital abnormality or birth defect.

**Note:** A planned hospitalization for pre-existing condition, or a procedure required by the CIP, without a serious deterioration in health, is not considered to be a serious adverse event.

#### 7.2 Procedure and/or Device Relationship

Determination of whether there is a reasonable possibility that the procedure and/or device involved in the registry caused or contributed to an adverse event is to be **determined by the Investigator** and recorded on the appropriate electronic CRF form. Determination should be based on assessment of temporal relationships, evidence of alternative etiology, medical/biologic plausibility, and patient condition (pre-existing condition).

#### 7.3 Adverse Event, Device Deficiency, and Complaint Reporting

##### 7.3.1 Adverse Event Reporting

###### General Adverse Event Reporting

Safety surveillance and reporting starts as soon as the patient has an attempted implant in the registry. An attempted implant is defined as insertion of the physiologic pacing lead into vasculature. Safety surveillance and reporting will continue until the last follow-up visit has been performed, the subject is deceased, the subject concludes

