### 6.2.1 Unsuccessful Implants and Device Explants

Sites will follow subjects who have an unsuccessful implant of the lead implanted for physiologic pacing for a period of 30 days for procedure-related adverse events and then withdraw the subject from the registry, unless the physiologic pacing lead implant will be re-attempted. Sites should submit all available data for the attempted implant through what was completed during the procedure.

Sites will follow subjects who have their device or lead implanted for physiologic pacing explanted for a period of 30 days for procedure-related adverse events, and then withdraw the subject from the registry.

Sites will withdraw subjects from the registry if a lead implant for physiologic pacing was not attempted – no data collection at implant or following implant is required.

All explanted Abbott devices and Abbott leads should be returned to Abbott to the address below:

Sites must complete and submit a Product Out of Service CRF for any explanted devices to Abbott using the EDC system. After 30 days, if the investigator will not re-attempt implant of a lead for physiologic pacing, sites must complete and submit a Withdrawal CRF and Adverse Event CRF (if applicable) to Abbott using the EDC system.

The physician may re-attempt to implant a lead for physiologic pacing and/or Abbott device at their discretion within 30 days of the initial attempted implant. If the physician chooses to re-attempt the implant, site must complete and submit the associated Implant visit CRFs, an Adverse Event CRF (if applicable) and a Product Out of Service CRF (if applicable) to Abbott using the EDC system.

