## Physiologic Pacing Registry Clinical Plan

### 6.3 Follow-up Assessments at 1 and 6 Months

The schedule of follow-up visits is based on the date of the successful implant of a lead for physiologic pacing with Abbott device implant. Table 2 outlines the time window permitted for each of the registry visits.

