**Table 2: Registry Time Interval Windows**

1 Month	6 Months
-14 days/+30 days	± 60 days

Sites will follow all subjects at 1 month and 6 months after the date of successful HBP lead and Abbott device implant.

During each follow-up visit, the following data will be collected:

- Follow-up related workflow
- Physiologic pacing capture and sensing thresholds
- For His placement only: Measured H wave using device IEGM
- Measured R wave using device IEGMs through lead implanted for physiologic pacing
- Presenting QRS duration and PR interval from 12-lead ECG
- QRS duration for all types of physiologic pacing captures observed from 12-lead ECG
- Incidence of increase in capture threshold of > 1V in leads implanted for physiologic or RV pacing leads
- Far-field atrial oversensing and ventricular oversensing and/or any interventions – including programming – required to address these issues
- NYHA Classification
- LVEF, LVEDV, LVESV (if available)
- Tricuspid and mitral regurgitation severity by echocardiogram (if available)
- Device estimated battery longevity via device session records
- Frequency/burden of detected atrial and ventricular arrhythmias via device session records
- Procedure and device-related adverse events and device deficiencies

Sites must download the device session records and submit to Abbott using the EDC system. Sites must also submit copies of the subject's physiologic pacing 12-lead ECGs in digital format (if available). Sites must complete and submit the associated Follow-up visit CRFs to Abbott using the EDC system.

Sponsor Representatives may provide support during the follow-up procedures for device-related data collection.

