3.2 Adverse Events

All of the adverse device effects, serious adverse device effects, UADEs, USADEs will be summarized for all subjects who enrolled in this trial in terms of the number of events and the percentage of subjects with events. Procedure and device related AEs will also be summarized.

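### Safety surveillance ends on a visit date rather than a fixed day, and the only adverse-event summary in the readable SAP is a crude percentage of all enrolled subjects that ignores unequal observation time

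*Protocol*

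**What the plan says.** **When surveillance opens and closes.** Protocol 7.3.1 states: "Safety surveillance and reporting starts as soon as the patient has an attempted implant in the registry". An attempt means that the lead has entered the vasculature. The end is defined by an occurrence, not a day: "Safety surveillance and reporting will continue until the last follow-up visit has been performed", or earlier at death, conclusion of participation or withdrawal. The last scheduled visit is at 6 months with a window of 60 days either way (Protocol 6.3, Tables 2 and 3). The visit clock has a different origin from the surveillance clock: "The schedule of follow-up visits is based on the date of the successful implant of a lead for physiologic pacing".

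**Early closures (Protocol 6.2.1).**
- Subjects with an "unsuccessful implant of the lead implanted for physiologic pacing for a period of 30 days for procedure-related adverse events" are followed that long and then withdrawn, unless a re-attempt is planned. A re-attempt is allowed within 30 days of the first.
- Subjects who have their "device or lead implanted for physiologic pacing explanted for a period of 30 days for procedure-related adverse events" are likewise followed and then withdrawn.
- Subjects in whom no lead implant was attempted are withdrawn, and no data at or after implant are required.

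**Analysis.** SAP 3.2 summarizes adverse device effects, serious adverse device effects and their unanticipated counterparts for all enrolled subjects "in terms of the number of events and the percentage of subjects with events". It adds that procedure- and device-related events will also be summarized. SAP 2.3.2 summarizes follow-up characteristics, which include these related events, at 1 and 6 months. SAP 2.2.3 plans Kaplan-Meier curves, with censoring at the last event-free time, for time-to-event variables, but names none. Protocol 8.2 makes survival analysis optional.

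**Comparison.** Protocol 4.1 and SAP 1.4 list procedure- and device-related adverse events as both an implant and a follow-up characteristic. Both say that implant and follow-up characteristics will be compared with and without EnSite.

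**The concern.** A crude percentage has a clear meaning when everyone is watched for the same length of time. Here two subjects who both keep to the schedule can differ two-fold in observed time: an event on day 150 is reportable in a subject seen on day 240 but not in one whose last visit was on day 120. Subjects closed early after a failed implant or an explant are watched for less time still. Those with no attempt are in the denominator but are never under surveillance. Protocol 5.7 puts participation at about 6 months, so a reader is likely to take the percentage as a 6-month risk.

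What is at stake is mainly the comparison by mapping use. Mapping follows site routine and is not randomized. If visit timing, or the share of failed or explanted leads, differs between the groups, their crude percentages can differ with no difference in risk.

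**Working it through.** The plan states no event rate, power or sample-size calculation (SAP 2.4), so there is no figure of its own to reproduce. The 5% risk at day 180 below is an assumption, used only to show size.

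**1. Closing window.** Taking 6 months as 180 days: 180 − 60 = 120 and 180 + 60 = 240, a ratio of 2.0. Taking it as 183 days gives 123 to 243. These count from the successful implant. After a re-attempt up to 30 days later, observation from the first attempt could reach about 240 + 30 = 270 days.

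**2. Constant hazard.** λ = −ln(0.95)/180 = 0.000285 per day, and F(t) = 1 − exp(−λt). This gives F(30) = 0.85%, F(120) = 3.36%, F(150) = 4.18%, F(180) = 5.00%, F(210) = 5.81% and F(240) = 6.61%.

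**3. Front-loaded hazard.** Let H = −ln(0.95) = 0.0513 and put a share s of H in the first 30 days, with the rest spread evenly over days 30 to 180 and continuing at that rate. For t ≥ 30, F(t) = 1 − exp{−H[s + (1 − s)(t − 30)/150]}. For s = 0.8, day 150 gives 1 − exp(−0.96H) = 4.80% and day 210 gives 1 − exp(−1.04H) = 5.19%.

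| Share of hazard in first 30 days | Day 120 | Day 150 | Day 210 | Day 240 | Ratio 210/150 | Ratio 240/120 |
|---|---|---|---|---|---|---|
| Constant hazard (30/180) | 3.36% | 4.18% | 5.81% | 6.61% | 1.39 | 1.97 |
| 50% | 4.02% | 4.51% | 5.49% | 5.97% | 1.22 | 1.49 |
| 80% | 4.61% | 4.80% | 5.19% | 5.39% | 1.08 | 1.17 |
| 90% | 4.80% | 4.90% | 5.10% | 5.19% | 1.04 | 1.08 |

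**4. Pooled rate.** If closing days spread evenly over days 120 to 240, the mean of F(t) under constant hazard is 4.995%, against 5% at day 180.

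**5. Early closure.** If 10% of subjects closed at day 30 under constant hazard, the crude figure would be 0.90 × 5.00% + 0.10 × 0.85% = 4.59%. This suits failed implants poorly, since 6.2.1 follows them for procedure-related events, which would tend to fall near the procedure.

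**6. Denominator.** If 5% of enrolled subjects never had an attempt, 5% would be reported as 0.95 × 5% = 4.75%. The 10% and 5% shares in steps 5 and 6 are assumptions.

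**The case against.** The strongest reply is that this is a descriptive registry with no hypothesis test, and that the effect is small where it can be judged. Much of that stands. The pooled percentage is almost unchanged if visits centre on 6 months (step 4). For events close to implant, even the extreme contrast shrinks to 1.08–1.17 (step 3).

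A reader might also infer more than the documents support:

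- *That rates are distorted nearly two-fold.* The ratio of 1.97 needs a constant hazard, with one group closing entirely at day 120 and the other entirely at day 240.
- *That mapping sites see patients earlier or later.* Nothing says so. The protocol sets the visit schedule, and no readable text links timing to mapping.
- *That every explanted lead closes at day 30.* The 30 days most naturally run from the explant, so an explant at month 4 closes near month 5. Many such subjects may already have a reportable event, so it does not follow that a group with more explants looks safer.
- *That all-cause rates are affected.* Protocol 7.3.1 collects all serious events and deaths, but SAP 3.2 names no percentage for all-cause serious events or hospitalizations, and deaths appear in SAP 3.3 as a termination reason.
- *That the SAP has no time frame or survival method.* SAP 2.3.2 gives visit-based 1- and 6-month summaries, and 2.2.3 gives Kaplan-Meier with censoring. Neither fixes a day for adverse events.

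Finally, SAP 2.5 and 2.6 and Protocol sections including 8.2.1, 8.4 and 8.8 are redacted and could hold a relevant rule. SAP 3.2 itself is readable and specifies only counts and crude percentages.

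**Conclusion.** The point holds in limited form. Observation time is unequal by design, and the adverse-event summary specified in the readable text does not account for it, although the SAP already describes a method that would. The denominator also includes subjects who never enter surveillance.

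The overall rate is probably little affected. The exposure lies in the comparison by EnSite use for later events, and only if closing times or early closures differ between groups. A 60-day difference in closing day would show equal risk as 4.18% versus 5.81% (ratio 1.39) under a constant hazard and a 5% risk at day 180. With 50–90% of the hazard in the first 30 days, that ratio falls to 1.22–1.04. The documents give no evidence that such a difference will occur, so this is a cheap safeguard, not a demonstrated bias. Nor do they support the inference that sites must keep subjects under observation longer: the gain comes from the analysis.

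**What to change.** In SAP 3.2, add one paragraph:

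- Among subjects with an attempted implant, estimate by Kaplan-Meier the cumulative incidence of the first procedure- or device-related adverse event, and separately of the first serious adverse device effect.
- Count time from the attempted implant, censor at the end of surveillance, and report at day 30 and day 180, overall and by mapping use.
- Show numbers at risk. If visits spread evenly over the window, about half of the subjects who complete the visit will already be censored by day 180. Day 120 is the longest horizon that every in-window visit covers and could be shown as well.
- State that closure after a failed implant or an explant depends on clinical outcome and may be informative censoring, which Kaplan-Meier does not remove.
- Keep the crude counts and percentages alongside.

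The cost is a little more analysis using a method already in SAP 2.2.3, and a day-180 estimate that may be slightly less favourable than the crude percentage. No extension of site contact is required, and hence no Clinical Plan amendment or added work at up to 75 centers for that purpose. If a redacted section already contains such a rule, a cross-reference from SAP 3.2 is enough.

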## Physiologic Pacing Registry Clinical Plan

participation in the registry, or the subject withdraws from the registry. Sites will collect all serious adverse events (including all deaths) and all adverse events related to the procedure and/or device, whether serious or not, throughout the time period defined above and will report to the Sponsor on a CRF. Additional information regarding an adverse event should be updated within the appropriate CRF.

Unchanged, chronic, non-worsening or pre-existing conditions are not adverse events and should not be reported. An off-line form will be made available to allow the investigator to report serious adverse events in the event the entry cannot be made in the EDC. This does not replace the EDC reporting system. All information must still be entered in the EDC system as soon as feasible.

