### 1.1 Background and Rationale

#### 1.1.1 Background

Patients with cardiac disease may exhibit symptoms associated with electrical conduction abnormalities, such as bradycardia and/or sinus node dysfunction, thereby requiring implantation of a permanent dual-chamber (atrioventricular) or single-chamber (ventricular) pacemaker. However, these pacing modalities are associated with alteration of the normal electrical conduction due to right ventricular (RV) apical pacing, leading to accelerated progression of heart failure, and increasing the risk of heart failure hospitalization and atrial fibrillation. Patients with electrical conduction abnormalities may also present with associated ventricular dyssynchrony causing further cardiac disease progression into heart failure with impaired left ventricular function. The standard of care treatment for patients with ventricular dyssynchrony is implantation of a CRT system to activate the left ventricle and resynchronize the electrical conduction within the heart. However, CRT is not always feasible due to difficulty in placing the left ventricular lead. Furthermore, the percentage of CRT non-responders remains high, up to 30-40%.

An alternative and potentially more effective pacing strategy for patients with electrical conduction abnormalities is physiologic pacing. Physiologic pacing is achieved by delivering a pacing stimulus to a cardiac conduction structure, such as the bundle of His or left bundle branch (LBB) of the His-Purkinje system, with a permanent lead. Physiologic pacing activates the heart through the native His-Purkinje conduction system, thus offering the most

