#### 7.1 Definition

##### 7.1.1 Adverse Event

An adverse event is any untoward medical occurrence, unintended disease or injury, or untoward clinical signs (including abnormal laboratory findings) in subjects, users or other persons, whether or not related to the medical device under investigation.

**Note:** This definition includes events related to the procedures involved.

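### The exclusion of chronic or pre-existing conditions in protocol section 7.3.1 can be read to cover conditions that worsen, which conflicts with section 7.1

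*Protocol*

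**What the plan says.** Protocol section 7.3.1 sets the collection scope: "Sites will collect all serious adverse events (including all deaths) and all adverse events related to the procedure and/or device, whether serious or not". The next paragraph of the same section carves out background disease: "Unchanged, chronic, non-worsening or pre-existing conditions are not adverse events and should not be reported".

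The definitions come earlier. Section 7.1.1 states: "An adverse event is any untoward medical occurrence, unintended disease or injury, or untoward clinical signs", and makes no exception for patients who already have the disease in question. Section 7.1.2 builds seriousness on top of that: "If the adverse event meets any of the criteria below, it is regarded as a serious adverse event". Its criteria include serious deterioration in health resulting in, among other things, "in-patient hospitalization or prolongation of existing hospitalization, or" and other listed outcomes. A note to 7.1.2 says that a planned admission for a pre-existing condition is not a serious adverse event, provided that health has not seriously deteriorated.

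Procedure- and device-related adverse events are listed as both implant and follow-up outcome measures (protocol 4.1; SAP 1.4). SAP 3.2 summarises them from what sites report.

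**The concern.** The four descriptors in the 7.3.1 sentence are joined by *or*, and each modifies *conditions*. Grammatically, a condition that is chronic, or one that was present before implant, meets the exclusion whether or not it has changed. The patients enrolled are due to receive a pacemaker, a defibrillator or a CRT device, so they arrive with cardiac disease. Worsening of existing disease is therefore an ordinary form for an adverse event to take in this registry.

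If a site follows the sentence literally, a worsening that it judges related to the device or procedure may never reach the Adverse Event form. It would then be missing from a listed registry outcome and from the SAP 3.2 summary. Sites that take the sentence to mean stable disease would report the same event. The reported rates would then partly reflect how each site reads one line of the plan.

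**Working it through.** No arithmetic applies. The documents give no event rates, and the SAP (2.4) has no hypothesis test or sample size calculation on which this could bear. The check is a comparison of the texts.

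**Step 1: the two readings of the 7.3.1 sentence.**
- *Stable-disease reading.* *Unchanged* and *non-worsening* govern the whole list, so only background disease that has not moved is excluded. This gives every word a function, but it needs *or* to work as *and*.
- *Literal reading.* Any one descriptor is enough. A pre-existing condition is excluded even when it worsens.

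No sentence in section 7 settles the choice by stating that worsening of a pre-existing condition is an adverse event.

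**Step 2: the literal reading against 7.1.1.** The definition takes in "any untoward medical occurrence, unintended disease or injury, or untoward clinical signs". A worsening is an untoward occurrence, so 7.1.1 includes what the literal 7.3.1 sentence removes.

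**Step 3: the literal reading against 7.1.2.** The note exempts only planned admissions without serious deterioration. By implication, serious deterioration of a pre-existing condition counts. The literal 7.3.1 sentence says that it does not.

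**Step 4: whether the duty to collect all serious events cures this.** Not by itself. Section 7.1.2 applies the seriousness test to something that is already an adverse event. Under the literal reading, 7.3.1 says that the condition is not one, so it would drop out before that test and before the three-day reporting rule.

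**Step 5: which events are exposed.**

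| Worsening of a pre-existing condition | Position under the plan |
|---|---|
| Serious, including unplanned admission | Covered by the 7.1.2 criteria and note and by the 7.3.1 duty to report serious events. Lost only if a site applies the literal list against the 7.1.2 note. |
| Non-serious, related to procedure or device | Within 7.1.1 and the 7.3.1 scope, but no note or criterion speaks for it. Most exposed. |
| Non-serious, unrelated | Outside the 7.3.1 scope in any case. The sentence makes no difference. |

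**Step 6: what other data would still show.** NYHA class and device-recorded arrhythmia burden are collected at each follow-up visit (6.3). Table 3 schedules a hospitalization assessment at 1 month, 6 months and unscheduled visits. These would show some of the worsening. They do not carry the investigator's relatedness judgement (7.2), and they are not adverse event reports. The hospitalization assessment is not in the 6.3 follow-up list or among the SAP 1.4 endpoints.

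**The case against.** The strongest reply is that the sentence is loose but its meaning is plain. If *pre-existing* alone barred reporting, *unchanged* and *non-worsening* would do almost no work. The sentence also speaks of conditions, whereas 7.1.1 speaks of occurrences: heart failure is a condition, and an acute decompensation is a new occurrence. Section 7.2 asks the investigator to weigh the patient's pre-existing condition when judging relatedness, which assumes that events in such patients reach the form. Serious worsening is addressed by the deterioration and hospitalization criteria and by the duty to report all serious events.

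Much of this stands. The stable-disease reading is probably what was intended, many sites will adopt it, and serious worsening is the best-protected case. It does not remove the point, because the intended reading has to be inferred and the literal one contradicts 7.1. The inference is weakest for non-serious related worsening, where the 7.1.2 note gives no help.

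A reader might go further and infer that the plan keeps out of its safety data the very harm that its background describes. The documents do not support that. Section 1.1.1 does speak of pacing "leading to accelerated progression of heart failure, and increasing the risk of heart failure hospitalization and atrial fibrillation", but it attributes this to right ventricular apical pacing and presents physiologic pacing as the alternative. Hospitalized heart failure would in any case meet the 7.1.2 criteria. Nor does the *chronic disease* item in 7.1.2 strengthen the case: there it is an outcome of an event, not a description of background disease.

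**Conclusion.** The point holds as an ambiguity in a reporting rule. Followed literally, section 7.3.1 drops events that section 7.1 includes, and it bears on a listed registry outcome. Severity is minor. The practical exposure is mainly non-serious, procedure- or device-related worsening of a pre-existing condition, at sites that take the list word for word.

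Two larger conclusions are tempting and should not be drawn:

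- **A count of lost events.** A reader might combine the SAP 1.3 ceiling of 1,000 subjects with assumed figures, for example 30% to 50% with prior heart failure and a 3% to 8% six-month risk of hospitalized worsening. That gives 1,000 × 0.30 × 0.03 = 9 to 1,000 × 0.50 × 0.08 = 40. Neither percentage is in the documents. The calculation also assumes that every site reads the sentence literally, and it counts the serious events that the plan protects best. It does not measure this problem.
- **Bias in the EnSite comparison.** Mapping follows site routine, so a site-level difference in reporting could carry over. That would require sites' reading of this sentence to be associated with their use of mapping, and nothing in the documents shows that it is. The SAP plans only descriptive summaries of these characteristics (2.3.1, 2.3.2).

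The verdict assumes that at least some sites could reasonably apply the literal reading. The documents cannot say how many would.

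**What to change.** Reconcile 7.3.1 with 7.1.1 and 7.1.2. Limit the exclusion to chronic or pre-existing conditions that remain unchanged and are not worsening. Add that worsening in severity or frequency after the attempted implant is an adverse event, to be reported under the scope that 7.3.1 already sets: serious, or related to the procedure or device. The starting point matches 7.3.1, where safety surveillance begins at the attempted implant.

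This changes reporting text only and leaves patient care as it is. It needs one sentence in the Clinical Plan and a note in site training, and it uses the existing Adverse Event form. The hospitalization assessment in Table 3 can serve as a completeness check for serious events. The downside is slightly more adverse event entry and a slightly higher reported event rate.
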